##### **4.2.12.1 EORTC QLQ-C30**

Time to symptom deterioration will be analyzed for each of the 3 symptom scales (fatigue, pain, and nausea/vomiting). Time to HRQoL/function deterioration will be analyzed for the 5 function scales (physical, role, emotional, cognitive, and social) and global health status/QoL.

This will be achieved by comparing treatment arms using a stratified log-rank test as described for the PFS and OS analysis. The effect of MEDI4736 monotherapy versus SoC and MEDI4736 + tremelimumab combination therapy versus SoC treatment will be estimated by the HR together with its corresponding 95% CI using stratified Cox model with the same approach as described for PFS and OS analysis.

Time to deterioration will be presented using a Kaplan-Meier plot for each of the 3 symptom scales (fatigue, pain, and nausea/vomiting), 5 functional scales (physical, role, emotional, cognitive, and social), and global health status/QoL.

A summary of the symptom improvement rate for each of the 3 symptom scales (fatigue, pain, and nausea/vomiting) items will be produced. Similarly, a summary of HRQoL/function improvement rate for each of the 5 function scales (physical, role, emotional, cognitive, and social) and global health status/QoL will be produced. Symptom improvement rate for each of the 3 symptom scales (fatigue, pain, and nausea/vomiting) and HRQoL/function

improvement rate for each of the 5 function scales (physical, role, emotional, cognitive, and social) and global health status/QoL will be analyzed by comparing between treatment arms using a logistic regression model as described for the analysis of ORR.

Summaries of absolute and change from baseline values for each of the 3 symptom scales/items (fatigue, pain, and nausea/vomiting), 5 individual symptom items (dyspnea, insomnia, appetite loss, constipation, and diarrhea), 5 functional scales (physical, role, emotional, cognitive, and social), and the global health status\QoL score will be reported by visit for each treatment arm provided at least one treatment arm has 20 or more subjects with data at a given visit. Graphical presentations may also be produced as appropriate.

Analysis of HRQoL or symptom will also be carried out by comparing mean change from baseline in the global health status/QoL, functions (physical, role, cognitive, social and emotional) scores (from the EORTC QLQ-C30 questionnaire) between MEDI4736 + tremelimumab combination therapy versus SoC and MEDI4736 monotherapy compared versus SoC. The analysis population for mean change in HRQoL or symptoms data will be the FAS (ITT) set and will include all randomised patients with an evaluable baseline assessment and at least one evaluable post baseline assessment.

Change from baseline will be derived using a MMRM analysis of all the post-baseline scores for each visit. The model will include treatment, visit, and treatment by visit interaction as explanatory variables and the baseline score and baseline score by visit interaction as covariates. Adjusted mean estimates per treatment group and corresponding 95% CIs will be presented along with an overall estimate of the treatment difference, 95% CI and p-value. An overall adjusted mean estimate will be derived that will estimate the average treatment effect over visits giving each visit equal weight using least squares means.

An unstructured matrix for the within-subject error variance-covariance will be used. If the model fit fails to converge, more parsimonious covariance structures will be considered to model the correlation between time-points from same patient. The following covariance structures will be tried in order until convergence is reached: Toeplitz with heterogeneity, autoregressive with heterogeneity, Toeplitz, autoregressive and compound symmetry. If either the autoregressive with heterogeneity or autoregressive structure is used, patient will be included as random effect.

The Kenward-Roger approximation will be used to estimate denominator degrees of freedom (DDFM). Restricted maximum likelihood (REML) estimation will be used.

The analysis will be performed on all post-baseline visits up to the latest scheduled visit where 20 or more ( $\geq 20$ ) patients on each treatment arm have a score.

Summary measures of overall compliance and compliance over time will be derived for the EORTC QLQ-C30. These will be based upon the compliance derivation described in Section [3.4.1](#)

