8.5.2.2 Objective response rate

The ORR will be based on the programmatically derived RECIST 1.1 using investigator assessment data. The ORR will be compared between MEDI4736 monotherapy versus SoC, MEDI4736 + tremelimumab versus SoC, and MEDI4736 + tremelimumab versus MEDI4736 monotherapy using logistic regression models adjusting for the same factors as the primary endpoint (PD-L1 status, tumor location, and smoking history). The results of the analysis will be presented in terms of an odds ratio together with its associated profile likelihood 95% CI and p-value (based on twice the change in log-likelihood resulting from the addition of a treatment factor to the model). This analysis will be performed on the PD-L1 TC/IC high subgroup, low risk of EM subgroup and all-comers. The ORR will again be compared between MEDI4736 +/- tremelimumab versus SoC using logistic regression models for the ctDNA TMB high (≥ 16 mut/Mb) subgroup.

CCI

Summaries will be produced that present the number and percentage of patients with a tumor response (CR/PR). Overall visit response data will be listed and summarized over time for all patients (ie, the FAS). For each treatment arm, BoR will be summarized by n (%) for each category (CR, PR, SD, PD, and NE). No formal statistical analyses are planned for BoR.

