### **Symptom improvement rate**

The symptom improvement rate will be defined as the number (%) of patients with 2 consecutive assessments at least 14 days apart that show a clinically meaningful improvement (a decrease from baseline score  $\geq 10$  for EORTC QLQ-C30 symptom scales) in that symptom from baseline. The denominator will consist of a subset of the FAS who have a baseline symptom score  $\geq 10$ .

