#### 4.1 General principles

IVRS based stratification factors will be used for the analysis of primary objectives as well as the analyses for other secondary objectives namely; PFS, ORR, PFS2, TFST, TSST, Time to

deterioration of EORTC QLQ-C30 and EORTC QLQ-H&N35, improvement rate of EORTC QLQ-C30 and EORTC QLQ-H&N35.

The subgroup analyses for the stratification factors as well as all other factors will be based on values recorded on the CRF. If there is >10% discordance in stratification factors as recorded in IVRS versus the Case Report Form (CRF), then a sensitivity analysis of the primary objectives, will be performed using CRF based stratification factors. For this sensitivity analysis if there are missing baseline covariate values, patients will be retained in the analysis by including the missing data as another stratification level.

Other general principles that will be followed throughout the study include the following:

- Descriptive statistics will be used for all variables, as appropriate, and will be presented by treatment group. Continuous variables will be summarized by the number of observations, mean, standard deviation, median, minimum, and maximum. Categorical variables will be summarized by frequency counts and percentages for each category.
- Unless otherwise stated, percentages will be calculated out of the population total for the corresponding treatment arm.
- For continuous data the mean and median will be rounded to 1 additional decimal place compared to the original data. The standard deviation will be rounded to 2 additional decimal places compared to the original data. Minimum and maximum will be displayed with the same accuracy as the original data.
- For categorical data, percentages will be rounded to 1 decimal place.
- Results of all statistical analysis will be presented using a 95% confidence interval (CI) and 2-sided p-value, unless otherwise stated.
- All models will include 3 treatment groups and any pairwise comparisons will then be extracted.
- SAS® version 9.4 or higher will be used for all analyses.
- Palliative radiation will not be considered as a subsequent therapy.

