#### **4.2.4 Objective response rate**

The ORR will be based on the programmatically derived RECIST 1.1 using site investigator tumor data. The ORR will be compared between MEDI4736 monotherapy versus SoC using logistic regression models adjusting for the same factors as the primary endpoint (PD-L1 status, tumor location, and smoking history). The results of the analysis will be presented in terms of an odds ratio together with its associated profile likelihood 95% CI (e.g. using the option 'LRCI' in SAS procedure GENMOD) and p-value (based on twice the change in log-likelihood resulting from the addition of a treatment factor to the model).

A similar analysis will be performed for the comparison between MEDI4736 + tremelimumab combination versus SoC and between MEDI4736 + tremelimumab combination versus MEDI4736 monotherapy in for the analysis populations detailed in Table 12.

Summaries will be produced that present the number and percentage of patients with a tumor response (CR/PR). Overall visit response data will be listed and summarized over time for all patients (i.e., the FAS).

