#### 4.2.12.2 EORTC QLQ-H&N35

Time to symptom deterioration for each of the 4 symptom scales/ items in the QLQ-H&N35 (pain, swallowing, senses and speech) will be compared between treatment arms using a stratified log-rank test as described for the primary analysis of OS. The effect of MEDI4736 monotherapy vs SoC and MEDI4736 + tremelimumab combination therapy versus SoC treatment will be estimated by the HR together with its corresponding 95% CI using stratified Cox model with the same approach as described for PFS and OS analysis.

For each of these 4 symptom scales/ items in the QLQ-H&N35 above, time to deterioration in symptoms will be presented using a Kaplan-Meier plot.

A summary of the symptom improvement rate for each of the 4 symptom scales/items (pain, swallowing, senses and speech) will be produced. The symptom improvement rate for each of the 4 symptom scales/items (pain, swallowing, senses and speech) will be compared between treatment groups using a logistic regression model as described for ORR.

Summaries of absolute and change from baseline values for each of the 7 symptom scale/item (pain, swallowing, senses, speech, social eating, social contact and sexuality) and 11 single-item measures (teeth, problems with mouth opening, dry mouth, sticky saliva, coughing, feeling ill, use of analgesics, use of nutritional supplements, use of a feeding tube, weight gain, and weight loss) will be reported by visit for each treatment provided at least one treatment arm has 20 or more subjects with data at a given visit. Graphical presentations may also be produced as appropriate.

The assessment of symptoms comparing mean change from baseline using the MMRM as described for EORTC QLQ-C30 will be repeated for pain, swallowing, senses, and speech of the EORTC QLQ-H&N35. All assumptions and outputs as described for the EORTC QLQ-C30 are applicable and the same approach from EORTC QLQ-C30 will be applied.

Summary measures of overall compliance and compliance over time will be derived for the EORTC QLQ-H&N35. These will be based upon the compliance derivation described for EORTC QLQ-C30

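### The PRO improvement-rate models leave out the scale's baseline score, so a valid supportive analysis gives up some precision and leaves chance baseline imbalance uncorrected

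*SAP*

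**What the plan says.** SAP 3.4.1 defines symptom improvement for QLQ-C30 as "2 consecutive assessments at least 14 days apart that show a clinically meaningful improvement", meaning a fall of at least 10 points from baseline. The denominator is patients with a baseline symptom score of at least 10. For function and global health the direction is reversed and the denominator is a baseline of at most 90. SAP 3.4.2 uses the symptom rule for QLQ-H&N35.

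SAP 4.2.12.1 says the QLQ-C30 improvement rates "will be analyzed by comparing between treatment arms using a logistic regression model as described for the analysis of ORR". SAP 4.2.12.2 says the QLQ-H&N35 rates "will be compared between treatment groups using a logistic regression model as described for ORR". The ORR model, in SAP 4.2.4, is a logistic regression "adjusting for the same factors as the primary endpoint (PD-L1 status, tumor location, and smoking history"). Protocol 8.5.2.2 names the same three factors, and Protocol 8.5.3.1 and 8.5.3.2 make the same cross-reference. SAP 4.1 lists the "improvement rate of EORTC QLQ-C30 and EORTC QLQ-H&N35" among the analyses that use IVRS stratification values and mentions no baseline score. No other section adds one.

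For mean change from baseline, by contrast, the MMRM in SAP 4.2.12.1 includes "the baseline score and baseline score by visit interaction as covariates".

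**The concern.** ORR has no pre-treatment value of the outcome, so its model needs no baseline covariate. An improvement rate does have one: the outcome is computed from it, and the baseline score also sets how much room a patient has to improve. Among eligible patients, one with a symptom score just above 10 must become almost symptom-free to count, while one with a score of 80 can qualify at many follow-up values. When the ORR model is borrowed unchanged, a predictor of the outcome is dropped although it is held for every patient analysed.

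Two things are at stake. The treatment comparison is less precise than it could be with the same data. And PRO baseline score is not a stratification factor, so the arms can differ on it by chance, and the model does not correct for that. The gap recurs across 13 scales (nine QLQ-C30, four QLQ-H&N35) in two populations, all-comers and PD-L1 TC/IC high. In the smaller population the planned size is 86 per arm for monotherapy versus SoC, so chance imbalance is larger.

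**Working it through.** The plan states no expected rate, variance, correlation or power for any improvement rate, so there is no figure to reproduce. The check is a simulation of the endpoint as the SAP defines it.

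**From the documents**
- 190 per arm (all-comers) and 86 per arm (PD-L1 TC/IC high), monotherapy versus SoC: SAP Table 5.
- Improvement of at least 10 points at two consecutive assessments, baseline at least 10: SAP 3.4.1 and 3.4.2.
- Two-sided 5% (95% CI by default): SAP 4.1. Likelihood-ratio test: SAP 4.2.4.

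**Assumed**
- Scores from 0 to 100 in steps of 11.1, mean 40, SD 25.
- Three follow-up visits, with equal correlation r of 0.4, 0.6 or 0.75 among baseline and visits.
- Three binary stratification factors without prognostic value, and no missing data.
- A treatment shift of 8 points at 190 per arm or 12 points at 86 per arm.
- Two arms, although SAP 4.1 fits three and extracts the pairwise comparisons.
- 1,500 trials per setting. The Monte Carlo standard error is √(0.7 × 0.3 / 1500) = 1.2 points for a power near 70%, and √(0.05 × 0.95 / 1500) = 0.6 points for an error rate near 5%.

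**Models compared**
- As written: logit P(improve) = treatment + three stratification factors.
- Modified: the same plus the continuous baseline score.

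**Power**

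| Per arm | r | As written | With baseline | Gain (points) |
|---|---|---|---|---|
| 190 | 0.40 | 71.1% | 80.6% | 9.5 |
| 190 | 0.60 | 84.5% | 89.3% | 4.8 |
| 190 | 0.75 | 95.4% | 96.8% | 1.4 |
| 86 | 0.40 | 71.9% | 82.3% | 10.4 |
| 86 | 0.60 | 87.0% | 91.2% | 4.2 |
| 86 | 0.75 | 96.2% | 97.5% | 1.3 |

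At 190 per arm and r = 0.6, a baseline mean of 25 gives 83.1% to 87.5%, and score steps of 16.7 give 82.9% to 88.4%.

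**Type I error.** With no treatment effect, rejection rates run from 4.2% to 6.1% as written and from 3.9% to 6.3% with baseline.

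**Does the denominator rule already deal with baseline?** No. About 92% of simulated patients are eligible, and among them each 10 points of baseline multiplies the odds of improvement by 1.33 (r = 0.75) to 1.74 (r = 0.4).

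**Chance imbalance.** The between-arm difference in mean baseline has an SD of about 2.3 points at 190 per arm and 3.4 at 86 per arm. In the model as written, each point of difference moves the treatment log odds ratio by 0.026 to 0.049. The odds ratios per 10 points agree with this: ln(1.34)/10 = 0.029 and ln(1.70)/10 = 0.053. For a 2-SD imbalance, the shift is 2 × SD × slope:
- 190 per arm: 2 × 2.32 × 0.0264 = 0.12, up to 2 × 2.34 × 0.0488 = 0.23 (odds ratio factor about 1.13 to 1.25).
- 86 per arm: about 0.20 (2 × 3.4 × 0.030) to 0.32 (2 × 3.37 × 0.0477).

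With baseline in the model the slope is at most 0.009 per point, so the same imbalance moves the log odds ratio by 0.04 at most (2 × 2.21 × 0.0088).

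**Effect on the estimate.** At 190 per arm and r = 0.6, the mean log odds ratio goes from 0.66 as written to 0.77 with baseline. The second is a different, conditional quantity, not a corrected value of the first.

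**The case against.** The strongest reply is that this is a valid and common analysis of a supportive endpoint. Under SAP 4.1 only OS is formally tested and every other endpoint has a nominal p-value. SAP 4.2.12 identifies five PRO endpoints as secondary, all of them times to deterioration. Improvement rates have no planned power and no decision rule. All of this stands, and it is why the priority is low. SAP 4.1 does list improvement rates among other secondary objectives, but only to say which stratification values apply. It does not make them key endpoints.

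The denominators already remove patients with no room to improve. That also stands, but a gradient remains among those who are left.

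The MMRM already gives a baseline-adjusted comparison. This is right for global health status, the five functions and the four QLQ-H&N35 scales. It is not established for QLQ-C30 fatigue, pain and nausea/vomiting, which SAP 4.2.12.1 does not name for the MMRM (SAP Table 12 is worded more generally).

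Adding baseline changes the odds ratio, whereas in a linear model such as the MMRM it does not change the target difference. It also assumes linearity on the logit scale for a bounded score. Both are real but small costs, and the first should be stated in the SAP.

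A reader might infer that the omission biases the test or inflates its error. The simulation does not support that: over randomizations the test holds its level, and the confidence interval covers chance imbalance. A reader might also infer a much larger power gain by assuming a correlation of 0.7 between baseline and amount of improvement. With equal variances that correlation is √((1 − r)/2), so 0.7 implies r = 1 − 2 × 0.49 = 0.02. Follow-up scores would then be almost unrelated to baseline, which is implausible. The r values used above correspond to 0.55, 0.45 and 0.35.

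**Conclusion.** The omission is certain from the text. The improvement-rate models adjust for three stratification factors and not for the score from which improvement is calculated. The analysis remains valid, and neither the OS testing hierarchy nor the five PRO endpoints tested at 1% are affected. The loss is about 1 to 10 points of power and an uncorrected shift of roughly 0.12 to 0.32 in the log odds ratio under a 2-SD chance imbalance. The direction is secure. The size depends on assumed means, SDs, treatment shifts and correlations, none of which the documents give, and the power gain shrinks as follow-up scores track baseline more closely. This is a cheap improvement of low priority.

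**What to change.** In SAP 4.2.12.1 and 4.2.12.2, write out the improvement-rate model rather than referring to ORR, and state that it includes the continuous baseline score of the scale analysed in addition to the stratification factors. Add a note that the resulting odds ratio is conditional on baseline and not directly comparable with the crude rates or with an odds ratio not adjusted for baseline.

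The cost is a sentence in each section and one model term. No new data are needed and no patient is lost, since entering the denominator requires a baseline score. To count as prespecified, the change has to be made before results are seen.

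While editing, reconcile the function/QoL improvement denominator: Protocol 8.4.3.1 gives a baseline of at least 10, and SAP 3.4.1 gives at most 90. Only the SAP rule removes patients without room to improve by 10 points.

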Change from baseline will be derived using a MMRM analysis of all the post-baseline scores for each visit. The model will include treatment, visit, and treatment by visit interaction as explanatory variables and the baseline score as a covariate. Adjusted mean estimates per treatment group and corresponding 95% CIs will be presented along with an overall estimate of the treatment difference, 95% CI and p-value. An overall adjusted mean estimate will be derived that will estimate the average treatment effect over visits giving each visit equal weight using least squares means.

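### The MMRM for PRO mean change leaves out the randomisation stratification factors, so its reported standard errors may be slightly too large

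*SAP*

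**What the plan says.** Protocol 3.5 randomises 2:1:1 in blocks, with a separate list for each stratum. The strata are PD-L1 status, tumour location (with HPV status inside OPC) and smoking history.

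SAP 4.1 states where these factors enter the analysis: "IVRS based stratification factors will be used for the analysis of primary objectives as well as the analyses for other secondary objectives namely". The secondary analyses it goes on to name are ORR, PFS, PFS2, TFST and TSST and, for the PRO scales, time to deterioration and improvement rate. The mean-change model is not in that list. SAP 4.2.4 specifies for ORR "logistic regression models adjusting for the same factors as the primary endpoint (PD-L1 status, tumor location, and smoking history"), and SAP 4.2.12.1 and 4.2.12.2 apply the same logistic model to PRO improvement rates. Both sections also use a stratified log-rank test and a stratified Cox model for PRO time to deterioration.

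The mean-change model differs. SAP 4.2.12.1: "The model will include treatment, visit, and treatment by visit interaction as explanatory variables". Two baseline terms complete the SAP model: "explanatory variables and the baseline score and baseline score by visit interaction as covariates". Protocol 8.5.3.1 is the same apart from the baseline-by-visit term: "The model will include treatment, visit, and treatment by visit interaction as explanatory variables and the baseline score as a covariate". SAP 4.2.12.2 says the MMRM "will be repeated for pain, swallowing, senses, and speech of the" QLQ-H&N35 and that "the same approach from EORTC QLQ-C30 will be applied". The output is an overall treatment difference with a 95% CI and p-value. Table 12 of the SAP runs it in all-comers and in the PD-L1 TC/IC high subgroup.

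**The concern.** When randomisation is stratified on a factor that predicts the outcome, the design removes that factor's contribution from the treatment comparison. A model that leaves the factor out does not know this. It counts the factor's variance as residual error and reports a standard error larger than the estimate's real variability. Confidence intervals come out too wide and the test rejects less often than its nominal level.

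For the same scales and patients, the SAP takes the strata into account when it asks how long until deterioration and how many improve, but not when it asks how much the mean changed. No reason is given in the unredacted text. The December 2020 SAP amendment reopened this model to add the baseline-by-visit interaction and left the strata out. What is at stake is the width of the reported intervals for scales that include global health status, physical function, pain and swallowing, all of which are named in the secondary PRO objective.

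**Working it through.** The documents give no SD, effect size, power or precision for the MMRM, so there is no stated figure to reproduce. The omission is established by reading; its size needs an assumption.

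**Inputs.** 760 patients at 380:190:190 (SAP 1.3), with all three arms fitted together (SAP 4.1). Extra parameters if the factors enter as main effects: PD-L1 status 1, location/HPV in three levels 2, smoking 1, total 4. Assumed: R², the share of residual score variance explained by these factors after baseline, from 0% to 20%.

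**Reported standard error.** With factors divided by without factors, SE ratio = √(1 − R²). For example, √(1 − 0.05) = 0.975.

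**Real size of the unadjusted 5% test.** Under stratified blocking with complete data, the estimate's true SD is already about √(1 − R²) times the unadjusted model's SE. The test statistic is therefore under-dispersed, and its size is 2Φ(−1.96/√(1 − R²)). For R² = 10%: 1.96/0.949 = 2.066, giving 3.9%.

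| Assumed R² | SE ratio | Reported SE smaller by | Real size of nominal 5% test without the factors |
|---|---|---|---|
| 0% | 1.000 | 0% | 5.0% |
| 2% | 0.990 | 1.0% | 4.8% |
| 5% | 0.975 | 2.5% | 4.4% |
| 10% | 0.949 | 5.1% | 3.9% |
| 20% | 0.894 | 10.6% | 2.8% |

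**Simulation check.** Single-visit ANCOVA, 1,500 runs per setting, 760 patients, 12 strata, assumed prevalences, assumed blocks of 4. Reported SE ratios were 1.000, 0.975, 0.949 and 0.894 at R² of 0%, 5%, 10% and 20%, matching the formula. The true SD of the estimate barely moved (ratios 0.999 to 1.001). At R² = 20% the type I error was 3.2% without the factors and 5.1% with them. The Monte Carlo error is √(0.05 × 0.95/1500) = 0.6 percentage points, so the conservatism was clear only in that setting; at 10% or less it is too small for this simulation to show.

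**Cost if the factors predict nothing.** SAP 4.2.12.1 keeps visits with as few as 20 patients per arm, about 80 in all at 2:1:1 (20 + 20 + 40). In a simulated cross-section of 80 blocked patients the SE ratio was 1.005 at R² = 0, 0.979 at 5% and 0.955 at 10%. If drop-out has destroyed the balance, an approximate ratio at R² = 0 is √(1 + 4/(80 − 4 − 4 − 1)) = √(1 + 4/71) = 1.028; at 760 patients it is √(1 + 4/751) = 1.003. Main effects in an MMRM are estimated from all visits, so the 80-patient figure for one late visit overstates the cost to the overall comparison.

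**The case against.** The strongest reply is that this is a choice between two valid analyses. SAP 4.1 lists by name the analyses that use the strata, the Protocol omits them from this model too, and baseline score on the same scale is already adjusted for and will absorb much of what site, HPV or smoking would explain. The p-values are nominal and no study decision depends on them. All of that stands. It limits the consequence but does not explain why the mean-change model alone among the main PRO analyses ignores the strata.

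Four stronger readings are tempting, and the documents do not support them.

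- A reader might infer that every other efficacy and PRO model is stratified. The OS and PFS subgroup models in SAP 4.2.2 and 4.2.3 are unstratified, and Protocol 8.5.3.1 and 8.5.3.2 use an unstratified Cox model for the PRO deterioration hazard ratios. That last difference from the SAP is a separate item to reconcile.
- A reader might infer bias. There is none from the omission itself with complete data.
- A reader might translate the smaller SE into extra patients gained. Under stratified blocking the estimate is almost equally precise either way; what is lost is mainly reported precision. Some real gain is possible where blocks are broken, as in the TC/IC high subgroup or after drop-out. Simulated random retention of 45% or 20% of patients put the true SD ratio at roughly 0.97 to 0.99 for R² of 5% to 10%, with nothing detectable at 2%.
- A reader might argue that the strata are needed to make missing-at-random credible. Nothing in the documents shows that they predict drop-out, and SAP 4.2.12 already allows multiple imputation and pattern-mixture models if missing data are substantial.

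**Conclusion.** The point holds as an inexpensive improvement, not as an error. Both PRO MMRMs omit factors on which the trial is randomised and which the SAP's main OS, PFS, ORR and other PRO analyses respect. If those factors predict PRO scores beyond baseline, the reported standard errors are too large and the tests conservative: by about 0% to 5% in the SE for an assumed R² of 0% to 10%, and about 11% at 20%. That R² is an assumption, and zero cannot be excluded. The figures also assume additive factor effects, blocking that is largely intact, and a single visit as a stand-in for the repeated-measures model. The importance is low, because the MMRM is outside the multiple testing procedure and is not one of the five time-to-deterioration endpoints that SAP 4.2.12 tests at 1.0%.

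**What to change.** Add one sentence to SAP 4.2.12.1, carried into 4.2.12.2: the MMRM also includes, as fixed effects with IVRS values, PD-L1 status, tumour location/HPV in three levels (OPC HPV-positive, OPC HPV-negative, non-OPC) and smoking history. Add the MMRM to the list in SAP 4.1, and record the change from Protocol 8.5.3.1 in SAP section 6. If the sponsor prefers the present model, a sentence saying why would be enough.

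The cost is about four parameters and no new data. If the factors turn out not to be prognostic, the standard error rises negligibly: by about 0.5% in the simulated 80-patient cross-section, and by up to about 3% there if balance has been lost. In the TC/IC high subgroup, PD-L1 status will vary less, because everyone who enters through TC ≥50% is already positive at the 25% stratification cut-off; that term may contribute little there but does no harm.
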